7.3. Case Report Forms

All assessments and observations throughout the investigation must be carefully recorded in an electronic CRF (eCRF), or an application (Clinical Trial App) in a provided phone for each subject. Details about data capture can be found in section 10.1

7.4. Concomitant treatment

Concomitant treatment, including relevant medication, will be registered in the eCRF.

7.5. Supplementary materials and equipment (if applicable)

The Sponsor will provide the Principal Investigator, or delegate with supplementary materials for this investigation. Supplementary materials would be:

- Computer with access to CRFs
- Smartphone with Clinical Trial app.
- Nurse kits including disposal bags, gloves, gauze, disinfection gel etc.
- Tripod (a helping device to fixate the phone at virtual meetings)

8. Risk – benefit analysis and ethical considerations

8.1. Risk-benefit analysis of the investigational device

A risk analysis according to ISO 14971 Application of risk management to medical devices has been conducted. Risks have been proven minimized or eliminated through appropriate design control, confirmed by pre-clinical bench, laboratory and animal testing.

All unacceptable risks related to the device have been mitigated as far as possible and have been deemed acceptable for the clinical study.

8.2. Risk-benefit for subjects participating in the clinical investigation

The investigation is conducted in accordance with current law and applicable standards, see section 15. Statement of Compliance. The rights, safety and well-being of human subjects shall prevail over the interest of science of society.

Risks in this investigation are considered to be equal to the use of ostomy products already on the market. Risks associated with the use of ostomy products are skin irritation and mechanical trauma. Please also see Adverse events, adverse device effects and device deficiencies section 18.

There is no known interaction between the use of the test product and the medication participants can take – except from what is stated in the exclusion criterions. Disadvantages of testing may be the time spent on visits and responding questions regarding product change.

There is no benefits for the subjects in this investigation, except the test products should be able to notify the subject if leakage occurs, which could be beneficial for the subjects in regards to the quality of life and maybe minimize the worry about leakage. The outcome of this investigation will contribute with important information for development of products for subjects with a stoma.

8.3. Delegation of responsibility

Before initiation of the clinical investigation, sponsor must be provided with key personnel signed and dated curriculum vitae (not more than 2 years old) to verify their qualifications. Key site personnel are those, who treat or evaluate subject data in the clinical investigation. Also, the sponsor will ensure that all site personnel are trained in the investigation procedures, how to complete the CRFs, procedure for reporting an adverse event or serious adverse event (how, when, to whom), and who to contact in case of emergency related to the investigational device.

9. Monitoring

The sponsor is responsible for ensuring appropriate monitoring of the clinical investigation activities as described below.

The monitor will be the primary contact for the principal investigator and clinical investigation site personnel.

Monitoring activities are mandatory as per good clinical practice, however the extend and depth of these activities depend on the criticality of the clinical investigation, speed of enrolment, the experience of the clinical investigation site personnel in carrying out clinical investigations and specific study designs.

For the purpose of this clinical investigation the below described monitoring procedures have been determined.

9.1.1. Site selection visit

Depending on the prospective clinical investigation sites experience with the specific investigational device, an on-site qualification or site selection visit shall be performed during which the feasibility of the clinical investigation requirements will be discussed and common agreement between sponsor and principal investigator shall be reached. This visit may also be replaced by one or more phone calls if the principal investigator is known to the sponsor.

9.1.2. Initiation visit

The initiation visit will be held at Coloplast [name]. At the initiation visit, study personal will get a full training on all aspects of the clinical investigation incl. the use of the Investigator Site File. The initiation visit will be held as close to study start as possible.

9.1.3. Monitoring visit(s)

The site dedicated monitor is to ensure adherence to the clinical investigation plan, accurate data recording on the e-CRFs and to monitor recruitment rates and adherence to follow-up schedules. The principal investigator shall permit and assist the monitor to carry out verification of completed eCRFs against data in the source documents.

The principal investigator can delegate tasks to his/her collaborators, however the roles and responsibilities as time period of involvement for each clinical site personnel must be documented on the delegation log as well as training received before getting involved with the clinical investigation must be documented in the training log.

The monitor shall inform the sponsor about any problems relating to facilities, technical equipment or medical staff at the clinical investigation site. During the clinical investigation, monitors shall check that appropriate

written informed consents have been obtained. The monitor shall also be responsible for notifying such deficiencies in writing to the principal investigator and convene with the clinical investigation site personnel appropriate and timely corrective actions.

The sponsor, or delegate, will provide clinical monitoring, including review of eCRF with verification to the source documentation, as defined in the monitoring plan.

The monitor shall make written reports to the sponsor, after each visit and provide written action items if any, to the principal investigator or clinical investigation site personnel.

All data collected can be directly entered into the eCRF and the EDC system will via edit checks ensure that all fields are completed in the eCRF. Monitor will ensure by 100% monitoring, that all queries are timely resolved.

Source data verification will be performed to the extent it is possible. The Source Data Specification Form must be completed at the initiation visit detailing the location of the source data for each data point. Where no source data (besides the eCRF) is available the contents of the eCRF will be monitored.

The Informed Consent Forms, Letter of Authority and AE/ADE will be 100% monitored for timely completeness.

Only the investigator, delegated site personnel and the sponsor representatives will have access to all the eCRFs.

9.2. Source data verification

A source document is a document in which data collected for a clinical trial is first recorded. This data is usually later entered in the electronic case report form (eCRF). Source documents are defined as "original documents, data, and records". Source documents contain source data, which is defined as all information in original records and certified copies of original records of clinical findings, observations, or other activities in a clinical trial necessary for the reconstruction and evaluation of the trial.

All documents and data related to the clinical investigation handled by site personnel, shall be produced and maintained in a way that assures reliability, integrity, control and traceability, and shall be appropriately stored to provide a complete history.

The Principal Investigator shall assure the accuracy, attribution, completeness, legibility and timeliness of the data reported to the sponsor in the eCRFs and in all required reports. All printed copies of electronic source documents shall be certified, as indicated by a dated signature by the investigational site personnel at the time the document is printed. Special requirements should be applied to the capture, review and retention of electronic source data, to ensure reliability, quality, integrity and traceability.

The data reported in the eCRFs may be derived from source documents and be consistent with these source documents, and any discrepancies shall be explained in writing. In most cases, the eCRF will serve as the source document and this must be documented on the Source Data Specification Form. The Source Data Specification Form must be completed at the initiation visit detailing the location of the source data for each data point.

10. Statistical considerations

10.1. Statistical design, method and analytical procedures

Definition of analysis populations

Intention to Treat (ITT) and Safety populations will be defined at a formal data review meeting just before database lock. As a minimum, the data manager, the clinical manager and the statistician will be involved in the classification of subjects.

The ITT population (full analysis set) will be constituted by all included subjects who:

- Have provided valid informed consent
- Have information for at least one of the endpoints

The Safety population will constitute by subjects who have given informed consent.

All statistical analysis and summaries will be based upon the ITT population whereas adverse events and Device deficiencies will be assessed based on the safety population. Invalid individual data points may be omitted from analysis even though the corresponding subject is part of the ITT population. Any exclusion of data points will be documented.

A formal PP population is not planned due to the explorative nature of the investigation. Considering the data obtained it might however be considered to make additional explorative analyses based on a subset of the ITT population.

Analysis of endpoints, individual questions and baseline data

All endpoints and individual questions as well as baseline/demographic data will be listed and summarized by descriptive statistics. Summaries can be made for 1- and 2-piece users as well as for the subgroups (flat, convex and if relevant concave) or (iPhones, Androids), if relevant.

The accuracy of the sensor performance will be calculated based on picture data used to correlate notifications given with output to sensors on baseplates (primary endpoint). The accuracy will be calculated by dividing the true positive plus the true negative with the total sum of the true positive, true negative, false positive and false negative.

For secondary endpoints where the possible answer is Yes or No, the proportion of subjects answering "Yes" will be calculated. By use of an exact test in the Binomial distribution a 95% confidence interval will be estimated for the proportion. Further, it will be tested if the proportion is significantly different from 50% when using a 5% test level. For questions answered on a 5-point scale the answers can be grouped in 2 (e.g. "higher" or "much higher" against the rest of the answers) and analyzed by the above described method.

The total HRQoL score and the OLI sub scores will be analysed by a paired t-test to compare the results from Visit 1 (own product) and Visit 2 (own and test product).

The frequency of leakage on close before and after use of use of Olympus will be analysed by a Poisson loglinear model taken the paired design into consideration.

Users worry of leakage given on a 5-point scale will be analysed by a proportional odds ratio model taken the paired design into consideration to compare the results from Visit 1 (own product) and Visit 2 (own and test product)..

Other summaries and analyses can be made, if relevant.

As it is an exploratory study no adjustment for multiple testing will be applied.

All statistical analyses and summaries will be made with SAS version 9.4 (SAS Institute Inc., Cary, NC)

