6.4. Point of enrolment

A subject is considered enrolled in the investigation when the written informed consent is obtained. The expected duration for each subject is described in section 5.7

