7.1. Clinical investigation-related procedures

7.1.1. Visits

All visits (V) will be planned to be remote visits using Microsoft Teams, Skype or Face time, if technically possible. If a remote visit is not possible, a face to face meeting will be scheduled, either at subjects' own home or at Coloplast A/S, Humlebæk.

Visit 0 (Inclusion visit)

If a potential subject is interested in participating after the first contact and they met screening and inclusion criteria, a visit (visit 0) is arranged. When arranging the visit, it will be ensured, that the subject has received the Subject Information Form prior to the visit. The subjects will receive both written and verbal information to ensure that the subject understands what was read and explained and can freely agree to participate in the investigation. The subject will, beforehand, also be informed about the possibility of bringing a companion to Visit 0 and to any possible subsequent visits. During the visit the principal Investigator, or delegate, will provide oral information about the investigation based on the Subject Information Form. The subject has the right to wait before deciding on participation.

If/when subjects decide to participate, they will be asked to sign the Informed Consent Signature Form. Hereafter, relevant female subjects will be asked to take a pregnancy test. If a subject so desires, and it is certain that it is understood what the investigation entails, and the relevant form has been signed, the subjects are considered enrolled in the investigation. Enrolled subjects are allocated a subject number. Visit 0 and visit 1 can be combined.

Visits (V1)

During visit 1, baseline questions will be completed by the Principal Investigator, or delegate. The subject will be trained in the use of the clinical trial app, which is used for taking photos of used products at each product change, and how to complete the questions prompted at product change. The Principal Investigator, or delegate will ensure questions relevant for visit 1 are completed. At visit 1 the subjects will also thoroughly be trained in the use of the test product and instructed to continue their everyday life.

Visits (V2)

During visit 2, potential (S)AE's will be captured by the Principal Investigator, or delegate. During visit 2, the Principal Investigator, or delegate will ensure questions relevant for visit 2 are completed, hereafter termination.

Visits (Vx)

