18.2. Adverse device effect

An adverse event, which is related to the use of the investigational medical device, is an adverse device effect, and should be marked as related or possibly related on the adverse event form.

The definition of an adverse device effect includes any event resulting from insufficiencies or inadequacies in the instruction for use, deployment, implantation, installation and operation, or any malfunction of the medical device, as well as any event resulting from use error or from intentional misuse of the device.

Table 2 lists anticipated adverse device effects that may occur.

Table 2 Anticipated adverse device effects and their likely incidence rates

ANTICIPATED ADE	INCIDENCE RATE
Peristomal skin irritation (incl. mechanical trauma)	< 10%
Allergic peristomal skin irritation (dermatitis)	< 1%

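### The Safety population is defined by consent alone, so adverse device effect and device deficiency rates could be understated if any consented subject never uses the device

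*Combined protocol and SAP*

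**What the plan says.** Section 10.1 defines two sets. The ITT set requires consent and information on at least one endpoint. The Safety set requires consent only: "The Safety population will constitute by subjects who have given informed consent". Section 10.1 then assigns the safety data to it: "adverse events and Device deficiencies will be assessed based on the safety population".

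Four other places determine who can be in that set without using the device:

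- Section 6.4 fixes the point of enrolment at consent: "A subject is considered enrolled in the investigation when the written informed consent is obtained".
- Section 7.1.1 puts an eligibility check after the signature: "Hereafter, relevant female subjects will be asked to take a pregnancy test".
- The device comes later still: "At visit 1 the subjects will also thoroughly be trained in the use of the test product". The same section allows the gap to be closed: "Visit 0 and visit 1 can be combined". This is permitted, not required.
- Section 6.3 says that withdrawn subjects are not replaced.

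Section 18.2 ties a device effect to use: "An adverse event, which is related to the use of the investigational medical device, is an adverse device effect". It also gives expected incidences under the caption "Table 2 Anticipated adverse device effects and their likely incidence rates": below 10% for peristomal skin irritation and below 1% for allergic irritation.

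**The concern.** A subject who signs consent and then fails the pregnancy test, or withdraws before the test period starts, has no exposure to the device. That subject cannot add to the numerator of a device-effect rate but counts in its denominator. The error can only go one way, towards a lower rate.

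Neither the ITT set nor the data review meeting removes the problem. Some secondary and exploratory questions are answered at visit 1, so baseline answers alone could place a non-user in the ITT set. The meeting before database lock classifies subjects, but section 10.1 gives it no rule based on use.

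The stake is modest but real. Section 10.4 says the study will give insight into the safety of the device and that results may support claims, and section 21.1 reserves the data for reimbursement or regulatory use. With 25 subjects, a denominator that does not match those at risk is visible in the percentages.

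**Working it through.** The plan states no safety rate and no sample-size calculation, so there is no figure of its own to reproduce. The check is denominator arithmetic.

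**Inputs**

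- Consented subjects: 25, from section 6 (planned enrolment) read with section 6.4 (enrolment at consent).
- Replacement of withdrawals: none (section 6.3).
- u, the number of consented subjects who never use the device: not given. Assumed range 0 to 5.
- x, the number of subjects with at least one event: not given. Values 0, 2 and 3 are used for illustration.

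**Formulas**

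- Rate on the consented set: x/25.
- Rate on the exposed set: x/(25 − u).
- Relative understatement: 1 − (x/25) ÷ (x/(25 − u)) = 1 − (25 − u)/25 = u/25. It does not depend on x (for x above 0), and each non-user adds 1/25 = 4%.

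**Results** (exact Clopper-Pearson 95% intervals in brackets)

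| u | Exposed n | u/25 | x = 2 | x = 3 | x = 0, upper limit |
|---|---|---|---|---|---|
| 0 | 25 | 0% | 8.0% (1.0 to 26.0) | 12.0% (2.5 to 31.2) | 13.7% |
| 1 | 24 | 4% | 8.3% (1.0 to 27.0) | 12.5% (2.7 to 32.4) | 14.2% |
| 2 | 23 | 8% | 8.7% (1.1 to 28.0) | 13.0% (2.8 to 33.6) | 14.8% |
| 3 | 22 | 12% | 9.1% (1.1 to 29.2) | 13.6% (2.9 to 34.9) | 15.4% |
| 4 | 21 | 16% | 9.5% (1.2 to 30.4) | 14.3% (3.0 to 36.3) | 16.1% |
| 5 | 20 | 20% | 10.0% (1.2 to 31.7) | 15.0% (3.2 to 37.9) | 16.8% |

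The u = 0 row is what the consent-based rule reports whatever the true u. The other rows are what an exposed denominator would give.

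**Scale.** With two non-users and two events, the shift is 8.7 − 8.0 = 0.7 percentage points, against an interval on the consented set that is 26.0 − 1.0 = 25 points wide. With five non-users the shift is 10.0 − 8.0 = 2.0 points.

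**Against the anticipated rate.** Over the assumed range, the choice of denominator takes an observed rate from below 10% to 10% or above in one case only: 2 events with 5 non-users (2/25 = 8.0%, 2/20 = 10.0%).

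**Device deficiencies.** The arithmetic is the same, but u should then count consented subjects who never received the device. Section 18.3 gives a transmitter that will not charge as its example, and that fault can occur in a subject who has the device but has not yet applied a layer.

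**The case against.** The strongest reply is that nothing need go wrong. If every consented subject uses the device, the two denominators are the same. The plan also limits the number of non-users: section 6.2 has the criteria reviewed by phone before consent, and visits 0 and 1 may be combined. This stands. A reader might infer from section 10.1 that the reported rates will be diluted. The documents do not support that, because they neither give nor predict a number of non-users.

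Second, section 10.1 gives no rate formula, no safety endpoint is listed, and nothing tests results against the anticipated incidences. This also stands in part. A percentage of the safety set is the natural reading, but it is an inference. For the same reason, the documents do not support a reading that the rule would hide a safety signal or decide a claim.

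Third, a consent-based set suits adverse events in general. The flow chart in section 7.2 records them from screening, and section 18.1 covers events whether or not they are device-related. This stands, and it is why the consented set should be kept for listings.

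Fourth, a reader might conclude that one set, subjects who applied a sensor layer, should replace the consented set throughout. That goes too far. A fault found before first application may be the reason why no layer was applied, and such a set would drop that subject from the deficiency rate, again in the favourable direction.

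None of these replies supplies an exposure condition for device-effect rates.

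**Conclusion.** The point holds as a minor, conditional one. The Safety population has no condition on use, so any consented non-user stays in the denominator and can only lower a per-subject device-effect rate. The same applies to deficiency rates for a subject who never received the device.

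The size is a relative 4% per non-user: 0% with none, 20% with five of 25. These figures rest on three assumptions: 25 consented subjects, a number of non-users between 0 and 5, and rates calculated per subject in the safety set. In absolute terms the shift is at most 2.0 percentage points for two events (10.0 − 8.0) and 3.0 for three (15.0 − 12.0), well inside the exact intervals.

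**What to change.** Amend section 10.1 to state three denominators:

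- All consented subjects, for listing every adverse event from consent onward. A device-related event in someone who never applied a layer would still appear here.
- Subjects who applied at least one sensor layer, for adverse device effect rates.
- Subjects who received the device, for device deficiency rates.

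Report the number in each set beside the rates.

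The cost is a few sentences and no new data collection. The accountability records in section 14 already hold receipt, dates of use and subject identification, so both additional sets should be derivable. The downside is that the rates may become slightly less favourable.

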14	Confidence at night with test product com-pared to only using usual product	Subject				X	
15	Preference	Subject				X	
16	Reason for preference	Subject				X	
17	Evaluation of users' peace of mind with test product	Subject				X	
18	To evaluate users' assessment of QoL with test product compared to usual product	Subject				X	
19	Adhesive residue to skin	Subject				X	
20	Adhesive residue to transmitter	Subject				X	
	Exploratory endpoints						
Appx 1	HRQoL evaluation	Subject			X	X	
Appx 2	OLI evaluation	Subject			X	X	
21	Evaluation of self-management (predictabil-ity of change) of stoma appliance compared to usual product	Subject				X	

	Registration/measurement	PERFORMED BY	INFOR-MATION MEETING	SCREEN-ING	VISIT 1	VISIT 2 TERMI-NA-TION	CONTINUOUS LY
22							
23							
	Registration of termination						
	AEs/ADEs/SAEs/SADEs	Investigator		X	X	X	X
	Termination form	Investigator					X

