23.4. Appendix 4 – Questions

Assessment/endpoint	Question	Answer
Assessment		
Reason for change	What is the reason for change? Please tick ALL that apply.	
 • I follow my usual changing pattern • There is leakage under and outside the baseplate (soiling the clothes) • Due to a notification from the App • The entire baseplate is detached • The outer edge of the baseplate is detached • The center of the baseplate is detached • I am afraid the baseplate will detach • The area around the stoma is itching • The area around the stoma is painful • There is leakage under the baseplate (but not outside the baseplate) • The stoma bag is filled with air • There is a vacuum in the stoma bag • Other
Secondary endpoint(s)		
Frequency of leakage onto clothes	Think back on the last 3 weeks - how many times have you experienced leakage onto clothes?	Number
Overall experience of leakage onto clothes with test product compared to only using usual product	Compared with your usual product, to which degree have you experienced leakage onto your clothes with test product?	Fewer episodes of leakage onto clothes - More episodes of leakage onto clothes
Reliability of notifications	To which degree did you find the notifications from the App reliable and trustworthy?	Very high degree - High degree - Some degree - Low degree - Not at all
Ability to move with test product	Compared to your usual product, how was your freedom to move with test product?	Much better - better - Same - Worse - Much worse
Users worry of leakage	Think back on the last 3 weeks - to which degree have you worried about leakage?	Very high degree - High degree - Some degree - Low degree - Very low degree/Not at all

Confidence to avoid leakage onto clothes with test product compared to only using usual product	Compared to your usual product, did you feel confident that you could avoid leakage onto clothes?	Yes – No
Confidence in daily life compared to only using usual product	Compared to your usual product, to which degree did the test product give you confidence in daily life?	Much higher degree- Higher degree- Same degree - Lower degree- Much lower degree
Feeling of control with test product compared to only using usual product	Compared to your usual product, did test product give you a feeling of leakage control?	Yes, higher leakage control No, lower leakage control

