Control of leakage progression with test product compared to only using usual product	Compared to your usual product, did the test product give you a feeling of control of leakage progression?	Yes, higher control of leakage progression No, lower control of leakage progression
Feeling of security with test product compared to only using usual product	Compared to your usual product, did you feel more or less secure with test product?	I felt more secure – I felt less secure
Evaluation of confidence to increase social activities with test product compared to only using usual product	Compared with your usual product, did the test product affect your confidence to engage in social activities such as seeing friends, and do physical activities?	I felt more confident - I felt less confident
Evaluation of sleep with test product compared to only using usual product	Compared with your usual product, did the test product affect your sleep?	Yes, to the better Yes, to the worse No, the same
Confidence at night with test product compared to only using usual product	Compared with your usual product, to which degree did the test product give you confidence at night?	Much higher - Higher - Same - Lower - Much lower
Preference	Which product solution do you prefer?	Own product - Own product with test product
Reason for preference	What is your reason for preference? (Please tick all that apply)	
 • Body fit • Ability to bend and stretch • Feeling of security • Feeling of confidence • Less fear of leakage onto clothes

		
 • Discreet to wear • Discreteness in leakage control • Better sleep • Less embarrassment • Other text
Preference	How often would you use the test product?	Will never use it – Will use it rarely – Will use it sometimes – Will use it often – Will use it every day
Preference	If the test product was available today, would you start using it?	Yes – No
Preference	Would you recommend the product to others living with a stoma?	Yes – No
Evaluation of users' peace of mind with test product	To which degree did the test product give you peace of mind?	Very high degree- High degree- Low degree- Very low degree
To evaluate users' assessment of QoL with test product compared to usual product	Overall, do you think the test product can improve your feeling of control and confidence to avoid leakage onto clothes and therefore improve your quality of life?	Yes - No => if no, why not? Text

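### The tick list for reason for preference has only positively worded options, so a drawback of the device can be recorded as a reason only in free text

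*Combined protocol and SAP*

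**What the plan says.** The flow-chart (section 7.2, row 16) lists "Reason for preference" among the secondary endpoints, answered by the subject at Visit 2 only.

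Appendix 4 gives the instrument. The preference question has two answers, "Own product - Own product with test product", with no option for having no preference. The next question is "What is your reason for preference? (Please tick all that apply"). No branch by the product chosen is shown. There are nine fixed options: body fit, bending and stretching, security, confidence, "Less fear of leakage onto clothes", discreet to wear, discreteness in leakage control, better sleep and less embarrassment. A tenth entry is an open text field.

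On analysis, section 10.1 says "All endpoints and individual questions as well as baseline/demographic data will be listed and summarized by descriptive statistics", based on the ITT population. The subgroups it names are 1-piece/2-piece, baseplate shape and phone type. It adds "Other summaries and analyses can be made, if relevant". It has no rule specific to this question and none for coding the open text.

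Section 3.1 makes user experience in support of commercial claims a secondary objective, and section 10.4 allows results to be used for claims.

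**The concern.** A reason for preference can be a merit of the product chosen or a drawback of the one declined. The fixed list has room only for merits. A subject who chose the combination can tick what they liked about it. A subject who declined because the notifications were wrong or too frequent, the skin was uncomfortable, adhesive was left behind, or the transmitter was a burden to handle or charge has no box for that. They must type it, or tick a merit of their own product that may not be the real reason.

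Ticking takes less effort than typing, so the list makes it easier to record what favours the device than what counts against it. What is at stake is how this endpoint would read in a claim: a table of reasons with counts for benefits and, at best, uncoded remarks for drawbacks. The question is asked once, so options missing at Visit 2 cannot be added to the data later.

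There is also a smaller matter of tabulation. Several fixed reasons can be given for either product, so a percentage over all subjects does not say which product it speaks for.

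**Working it through.** The plan states no figure for this endpoint, so there is nothing to reproduce. The check is a reading of the option list, followed by an illustration with assumed numbers.

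**Step 1: sort the options (Appendix 4).**
- Can be ticked in favour of either product: body fit, bending and stretching, security, confidence, discreet to wear, better sleep, less embarrassment. That is 7 of 9, although security and confidence lie close to what the sensor is meant to offer.
- Fit only the sensor: less fear of leakage onto clothes, discreteness in leakage control. That is 2 of 9.
- Name a drawback of the device: 0 of 9.
- Open text: the only remaining route for a drawback.

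**Step 2: compare with other items in the same appendix.**
- The list for reason for change includes negative options (itching, pain, detachment) and a change prompted by an app notification.
- The sleep question has an answer for worse sleep.
- The quality-of-life question writes out a branch asking why not when the answer is no.

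So the instrument offers negative options and branches in other places. The preference-reason list has neither.

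**Step 3: does another item fill the gap?** Notification quality has its own question, "To which degree did you find the notifications from the App reliable and trustworthy", and residue to skin and to transmitter has two. Appendix 1 covers comfort and skin irritation. Adverse events and device deficiencies are reported separately. All of these measure whether a problem occurred. None records that the problem was why the subject preferred their own product.

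**Step 4: what an unsplit table could do (assumed tick rates).** Let n = 25, let k subjects prefer their own product, and let one reason be ticked by a share a of those preferring the combination and a share b of those preferring their own product.

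Pooled frequency = [(25 − k)a + kb] / 25

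Share of ticks from own-product preferrers = kb / [(25 − k)a + kb]

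| k | a = 30%, b = 80%: pooled | share of ticks | a = b = 50%: pooled | share of ticks |
|---|---|---|---|---|
| 5 | (6 + 4)/25 = 40% | 4/10 = 40% | 50% | 20% |
| 7 | (5.4 + 5.6)/25 = 44% | 5.6/11 = 51% | 50% | 28% |
| 10 | (4.5 + 8)/25 = 50% | 8/12.5 = 64% | 50% | 40% |
| 12 | (3.9 + 9.6)/25 = 54% | 9.6/13.5 = 71% | 50% | 48% |

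The row k = 7 is a useful marker. With 25 subjects, the exact two-sided test against 50% first reaches the 5% level when 18 prefer one solution (p = 0.043; 17 gives p = 0.108). A significant preference for the combination can therefore leave 7 subjects giving reasons for their own product.

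In whole counts, also assumed: 15 prefer the combination and 10 their own product, and discreet to wear is ticked by 2 and 6. Pooled, 8/25 = 32%, with 6/8 = 75% of the ticks from own-product preferrers. Split, 2/15 = 13% and 6/10 = 60%.

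When a = b, the pooled percentage equals the percentage in each group and is not distorted. The contrast therefore comes from the assumed rates, not from anything in the plan.

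**The case against.** The strongest reply has four parts.

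1. **Pooling.** A reader might infer that the plan merges reasons for and against the device into one table. The documents do not say so. Section 10.1 sets no table layout or denominator, it allows further summaries, and the subject listings would link each reason to the product preferred. A competent analyst would probably split the table. This stands: on tabulation, the only fault is that the split is not named.

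2. **Uncounted drawbacks.** A reader might also infer that reasons against the device are lost. They are not: the open text can hold them, and the notification, residue, sleep, comfort and quality-of-life questions, willingness to use the product, adverse events and device deficiencies all bear on them. This stands against the stronger reading. It does not close the gap in this endpoint, because those items do not record a reason for preference and no coding rule is given for the open text.

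3. **Balance.** Most of the fixed options can be ticked for either product, so own-product preferrers are not without boxes. That is true of merits. It does not provide a box for a drawback of the device.

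4. **Weight.** This is one of 19 secondary endpoints, descriptive, in an exploratory study with no formal hypotheses and no success criteria. This limits the importance of the point but does not remove it, since supporting claims is a stated purpose of the user-experience data.

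**Conclusion.** The point holds for the option list. Used as written, it records merits, including two that fit only the sensor, by tick, and drawbacks of the device only by free text. This rests on the wording of Appendix 4 and on no assumed number.

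The size of the effect is unknown. The documents give no expected preference split and no tick rates, and nothing on how often subjects would type a reason they cannot tick. The 13% versus 60% contrast and the 30%/80% table are illustrations only, and equal tick rates give no distortion of the pooled figure.

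The documents do not support saying that the plan pools the reasons, that drawbacks go unrecorded, or that a bias of known size exists. The primary endpoint, the sample size and the safety assessment are unaffected. The consequence is limited to claims drawn from this endpoint. It is still worth correcting before the study starts, because the tabulation can be settled at reporting but the missing options cannot be supplied after Visit 2.

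**What to change.** Before the first subject, add balanced options to the reason list in Appendix 4 and in the clinical trial app: reliable notifications and unreliable or too many notifications; skin comfort and skin discomfort; adhesive residue; extra handling or charging. Keep the open text field.

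As an accompanying clarification, add a sentence to section 10.1: reasons for preference are tabulated separately by preferred product, with the number of subjects preferring that product as denominator. It would help to say there how open-text reasons are grouped.

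The cost is a few answer options in the app, a somewhat longer list for subjects, and smaller denominators in each table. Section 12 gives changes to endpoints or assessment methods as examples of significant changes, so the sponsor should check whether the added options need notification.
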